7.7.1.3 Reporting Periods for Adverse Events and Serious Adverse Events

The safety reporting period for all AEs and SAEs is from study Day 1 (predose) through the EOT visit or 30 days after last study treatment (denintuzumab mafodotin or any component of RICE), whichever is later. However, all study protocol-related AEs are to be recorded from the time of informed consent. All SAEs that occur after the safety reporting period and are considered study treatment-related in the opinion of the investigator should also be reported to the sponsor.

SAEs will be followed until significant changes return to baseline, the event stabilizes (recovering/resolving) or is no longer considered clinically significant by the investigator, or the patient dies or withdraws consent. All non-serious AEs will be followed through the safety reporting period. Certain non-serious AEs of interest may be followed until resolution, return to baseline, or study closure.

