PET scans and computed tomography (CT) scans of the neck, chest, abdomen, and pelvis, will be assessed at baseline and at end of treatment (EOT). CT scans will be of diagnostic quality (i.e., contrast-enhanced with IV and oral contrast, unless contrast is medically contraindicated). Follow-up assessments will be performed at 3, 6, 12, 18, 24 months, and then annually after ASCT or EOT (for patients who don't receive ASCT). For all follow-up assessments, both PET and CT scans are required until disease is PET negative; responses will then be followed by CT scans of diagnostic quality. Follow-up assessments will continue until disease progression, initiation of a new anticancer treatment (with the exception of a stem cell transplant), or study closure, whichever occurs first.

At screening and/or at any time on study, if a bone marrow biopsy is performed as part of standard of care, the results from the biopsy report for the presence of lymphoma will be recorded in the case report form (CRF). A CT scan of diagnostic quality will be performed at the time of suspected clinical progression. Survival status follow-up will continue until patient death or study closure, whichever occurs first.

Subsequent ASCT is permitted, based on investigator discretion and standard of care, and is recommended to occur within 8 weeks of Cycle 3 Day 1 (Philip 1995). Data will be recorded to assess adequacy of hematopoietic stem cell collection and transplant.

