6.6 End of Treatment Visit

End of Treatment (EOT) visits should occur 14 to 30 days after the start of the last cycle (administration of denintuzumab mafodotin in the 19A+RICE Arm, or Day 1 of RICE in the control arm), unless delayed due to an AE. However, EOT evaluations must be performed before initiation of a new therapy, inclusive of radiotherapy and ASCT. If EOT evaluations are completed before 30 days after completion of study treatment, the patient will also be contacted 30–37 days following the completion of study treatment to assess for adverse events.

- Physical examination
- Review of inflammatory conditions (only for those patients with certain inflammatory conditions of interest at Screening/Baseline)
- ECOG performance status
- B symptom assessment
- ECG
- Ophthalmology exam (not required if an exam was performed within 4 weeks prior to the EOT visit, and following the last dose of study treatment)
 - Ocular health survey (± 2 days from the ophthalmology exam)
- Pregnancy test for females of childbearing potential
- Serum chemistry panel
- CBC with differential
- PT/PTT/INR
- Spot urine for UPC calculation
 - 24-hour urine collection if UPC > 2 (within 5 days after UPC assessment)
- Blood samples for PK, ATA, and biomarker assessments (see [Table 3](#))
- For patients discontinuing treatment due to disease progression: if a tumor biopsy was performed at the time of disease progression as part of standard of care, submit sample of tumor specimen, if available (see [Section 7.4.4](#))

The following response assessments are required (unless progressive disease [PD] was documented within the previous 6 weeks by diagnostic CT/PET scan):

- CT of diagnostic quality of neck, chest, abdomen, and pelvis (see Section 7.2)
- PET scan (Note: a combined CT/PET may be obtained to satisfy the requirements for CT and PET scanning, as long as the CT is of diagnostic quality)
- If patient is scheduled to undergo stem cell collection and bone marrow biopsy is performed as part of standard of care, record the bone marrow biopsy result for lymphoma involvement in the CRF.

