6.7 Long-Term Follow-Up Visits

Patients who discontinue from study treatment will remain on the study for follow-up until discontinuation from the study by withdrawal of consent, loss to follow-up, death, or study closure, whichever occurs first (see Section 4.3.2).

For patients who discontinue study treatment for any reason other than disease progression or initiation of a non-protocol therapy (with the exception of ASCT) for treatment of lymphoma, long-term follow-up visits for PFS assessment will occur at 3, 6, 12, 18, 24 months (± 1 month), and then annually after ASCT or EOT (for patients who don't receive ASCT).

The following assessments will be performed at long-term follow-up visits:

- Clinical assessment of disease status by history and physical examination
- CT scan of diagnostic quality of the neck, chest, abdomen, and pelvis (see Section 7.2) until disease progression or initiation of a new anticancer treatment (with the exception of a stem cell transplant); perform at follow-up visits and at any time disease progression is suspected
- PET scan, unless disease is PET negative; required until disease is PET negative (Note: a combined CT/PET may be obtained to satisfy the requirements for CT and PET scanning, as long as the CT is of diagnostic quality)
- Record subsequent anticancer therapies received
- For patients who receive ASCT, collect PBSC mobilization outcomes, and time to neutrophil and platelet engraftment

At any time during the follow-up period, if a bone marrow biopsy is performed as part of standard of care, the results from the bone marrow biopsy for lymphoma involvement will be recorded in the CRF.

For patients who proceed to ASCT, an ophthalmology exam and ocular health survey will be performed approximately 30-days post ASCT.

In addition, for patients who develop ocular toxicity during study treatment, ophthalmologic exams should be conducted monthly during the follow-up period (unless discussed with the medical monitor) until resolution or return to baseline.

All patients who receive at least one dose of denintuzumab mafodotin in the experimental arm or RICE in the control arm will be followed for survival at 6-month intervals after ASCT or EOT for the first 24 months and then yearly thereafter until death or study closure, whichever occurs first. At the time of study closure, patients will be contacted for a final survival assessment.

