7.6.1.1.1 Ocular AEs

Incidence, onset and improvement/resolution of ocular AEs of interest will be summarized based on the safety analysis set. The ocular AEs of interest will be defined by Standardised MedDRA Queries (SMQs) or Sponsor Specified Queries (SSQs) as appropriate. The

definition of the SSQs will be maintained in a separate document and will be finalized prior to database lock.

Patient incidence of treatment-emergent ocular AEs of interest will be presented by system organ class, preferred term and maximum severity. Ocular AEs leading to treatment discontinuation will be summarized.

Time to onset and duration to improvement or resolution will be summarized at the patient level for ocular AEs.

Date of onset is defined as the date of earliest occurrence of events of interest. Time to onset for will be summarized by descriptive statistics.

Improvement and resolution of ocular AEs will be derived per patient level. The date of resolution is defined as the earliest time that the patient does not have any ongoing ocular events (i.e. all events with outcome of resolved/recovered or resolved/recovered with sequelae, or all events with severity decreasing to baseline condition or better).

Improvement of ocular AEs is defined based on the worst grade for each patient. If a patient has worst grade 3 or 4 events, date of improvement or resolution is defined as the earliest date that the patient does not have any ongoing grade 3 or 4 events (i.e. the worst grade the patient is experiencing is 2 or below). If a patient has worst grade 2 ocular events of interest, the date of improvement or resolution is defined as the earliest date that the patient does not have any ongoing grade 2 events (i.e. the worst grade the patient is experiencing is 1 or below).

Time to improvement and resolution from first onset and from last treatment of 19A will be summarized for the patients who experienced ocular AEs of interest. Duration of ocular AEs may be summarized by Kaplan-Meier methodology. If a patient does not experience an improvement or resolution, the patient will be censored at last contact date for ocular symptoms, and censored at the date of last ophthalmology exam for corneal findings.

The relationship between ocular AEs and ocular interventions may be explored.

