7.6.6 Additional Safety Analyses

7.6.6.1 Ocular Examination Results

Ocular examination results will be presented in data listings. The improvement/resolution of corneal AEs may also be explored through visual acuity exam results.

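### AE reporting closes before the required post-transplant eye exam, so a new non-serious ocular event first found there need not be recorded as an AE

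*Protocol*

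**What the plan says.** **Reporting period.** Protocol 7.7.1.3 runs AE and SAE reporting from Day 1 predose "through the EOT visit or 30 days after last study treatment", where treatment means the ADC or any RICE drug, and takes the later of the two dates. Section 7.7.1.1 ties the recording of AEs, and of changes in their severity, to this period. The AE row of Appendix A stops at 30 days after the last dose.

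**Exceptions.** Section 7.7.1.3 still asks for SAEs that occur later and are judged treatment-related, and section 7.7.1.2 puts SAEs on the CRF. Section 7.7.1.3 also states: "Certain non-serious AEs of interest may be followed until resolution, return to baseline, or study closure". Ocular events are not named there.

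**Eye exams after treatment.** Section 6.7 states: "For patients who proceed to ASCT, an ophthalmology exam and ocular health survey will be performed approximately 30-days post ASCT". Patients who develop ocular toxicity during study treatment also have monthly exams until it resolves or returns to baseline. Appendix A note U adds post-ASCT collection of transplant-related data only.

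**Order of events.** Section 6.6 states: "End of Treatment (EOT) visits should occur 14 to 30 days after the start of the last cycle", unless an AE delays them, and requires EOT evaluations before ASCT. Section 3.1 says that ASCT "is recommended to occur within 8 weeks of Cycle 3 Day 1". Section 6.1 itself places ASCT after the reporting period.

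**Analysis.** SAP 7.6.1.1 names ocular AEs as the only AEs of special importance. SAP 7.6.1.1.1 says: "Incidence, onset and improvement/resolution of ocular AEs of interest will be summarized based on the safety analysis set", with incidence also shown by maximum severity. SAP 7.6.6.1 says of the exam data: "Ocular examination results will be presented in data listings"; it adds that visual acuity may be used to explore improvement or resolution of corneal AEs.

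**The concern.** The protocol schedules an eye exam in every transplanted patient but does not say whether a new finding there is an AE. The tables that describe the drug's main toxicity of interest are built from AE records, not from exam records. A late-onset event that is not serious may then appear only in a listing.

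This exam can carry real information. The EOT eye exam may be omitted if one was done in the previous 4 weeks and after the last dose (section 6.6), which the end-of-Cycle-3 exam can satisfy. For a transplanted patient without ocular toxicity on treatment, the post-ASCT exam may then be the next scheduled look at the cornea. Grade 1 corneal findings in Appendix E involve no change in visual acuity, so they may come to light only on examination.

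The plan is also uneven. SAP 7.6.1.1.1 follows corneal findings to the last eye exam when it measures time to improvement or resolution, so late recovery has a route into the analysis. Late non-serious onset has no required route.

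**Working it through.** The plan states no figure on this point, so the check is date arithmetic followed by a reading of the recording rules.

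**Step 1: timing.** Count days from Day 1 of the last cycle as 0.

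- L, last study treatment: 2 (Day 3), or 3 with the one-day window (sections 5.3.3 and 6.4.8).
- E, EOT visit: 14 to 30, later if delayed for an AE (section 6.6).
- A, ASCT: after E (section 6.6). The 8-week recommendation (section 3.1) gives 8 × 7 = 56.
- X, post-ASCT eye exam: A + 30 (section 6.7). The documents give no window around 30.

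Closure: C = max(E, L + 30).

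Gap: X − C = A + 30 − max(E, L + 30) = min(A + 30 − E, A − L).

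Because A > E, the first term exceeds 30. Because A > L, the second exceeds 0. With the exam at 30 days, the gap is therefore positive in every permitted sequence, including a delayed EOT.

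| Case | L | E | A | C | X | Gap (days) |
|---|---|---|---|---|---|---|
| Tightest permitted: earliest EOT, ASCT next day | 3 | 14 | 15 | 33 | 45 | 12 |
| ASCT at 8 weeks, last dose Day 3 | 2 | 14–30 | 56 | 32 | 86 | 54 |
| ASCT at 8 weeks, last dose Day 4 | 3 | 14–30 | 56 | 33 | 86 | 53 |
| EOT delayed to 45 (assumed), ASCT next day | 3 | 45 | 46 | 45 | 76 | 31 |
| Tightest case, exam at 23 days (assumed) | 3 | 14 | 15 | 33 | 38 | 5 |

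The tightest case is a calendar limit, not a likely course.

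**Step 2: what happens to a finding at that exam.**

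| Finding | Recording rule | Effect on the ocular AE tables |
|---|---|---|
| New, non-serious | None requires an AE record | Can be missing from incidence, onset and maximum grade |
| Worsening of an AE already recorded | Discretionary (7.7.1.3) | Patient stays in any-grade incidence for that term; maximum grade can be understated and time to resolution distorted |
| Treatment-related SAE | Reported, and on the CRF (7.7.1.2, 7.7.1.3) | Counted |
| Any late event a site chooses to record | Not required | Counted: the treatment-emergent definition has no upper time limit (SAP 7.6.1 and Appendix B) |

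The second row follows from SAP 7.6.1, which counts a patient once per preferred term. The last row means that capture of late non-serious events depends on site discretion, in a trial that is open-label (Protocol 3.2.3).

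**The case against.** A window of treatment plus about 30 days is a defensible choice. Protocol 3.2 names the decision to transplant and differences in conditioning as possible sources of bias, and events found after ASCT may come from the transplant rather than the drug. Nothing forbids a site from recording a late event, and the SAP would count it. The allowance for following AEs of interest uses the same label that SAP 7.6.1.1.1 gives to ocular AEs, and the SAP's censoring at the last eye exam implies that ocular status is carried into follow-up. Exam data may also be explored through visual acuity and VFQ-25.

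Much of this stands. A reader might infer that the plan bars everything found at the post-ASCT exam from the tables, or that late worsening drops out of incidence. The documents support neither: there is no exclusion rule, late treatment-related SAEs are captured, and a patient already counted for a term stays counted.

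What the objection does not supply is an instruction. The follow-up sentence is permissive and concerns AEs already recorded, and the SAP's censoring rule concerns resolution. Neither tells a site to record a new non-serious ocular finding. The optional analyses of visual acuity and VFQ-25 do not provide an incidence by arm.

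**Conclusion.** The point holds in a limited form. The reporting period closes before the post-ASCT eye exam in every transplanted patient, by about 12 days at the tightest and about 54 days with ASCT at 8 weeks. A new non-serious ocular event first found there has no recording requirement and can be missing from incidence. Late worsening is recorded at discretion and can affect only maximum grade and time to resolution.

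The timing rests on last treatment on Day 3 or 4, EOT before ASCT, and an exam at about 30 days. The size of any bias cannot be computed, because the documents give no rate of late-onset ocular events. A reader might take the 50% ASCT rate quoted in Protocol 1.1 and conclude that 0.50 × 100 = 50 patients are affected. That would be the number examined after closure, not the number with a lost event; the rate comes from a different trial, and Amendment 2 restricts new entry to early relapse.

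This is an inexpensive improvement to the safety reporting. It does not touch the primary comparison.

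**What to change.** In Protocol 7.7.1.3 and the AE row of Appendix A, require new or worsening ocular events, graded by Appendix E, to be recorded in both arms through the post-ASCT exam, and through the last monthly exam for patients followed for ocular toxicity. Make follow-up of ocular AEs mandatory rather than permitted.

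In SAP 7.6.1.1.1, keep the table for the current window as the main comparison. Add a second table of ocular incidence and maximum grade through the post-ASCT exam, by arm and by whether ASCT was received.

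The cost is a short protocol change, one Appendix A cell and one SAP table, with no new visit or exam. There are two downsides. Some late events will reflect transplant conditioning; the RICE arm, which has the same post-ASCT exam, helps to show how many. And only transplanted patients have this exam, so ascertainment depends on ASCT rates, which may differ by arm. The extended-window table should therefore be labelled descriptive.

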7.7.1.4 Serious Adverse Events Require Immediate Reporting

Within 24 hours of observing or learning of an SAE, investigators are to report the event to the sponsor, regardless of the relationship of the event to the study treatment regimen.

For initial SAE reports, available case details are to be recorded on an SAE form. At a minimum, the following should be included:

- Patient number
- Date of event onset
- Description of the event
- Study treatment, if known

The completed SAE form and SAE Fax Cover Sheet are to be emailed or faxed to the sponsor's Drug Safety Department (see email address or fax number included on the SAE report form) within 24 hours.

Relevant follow-up information is to be submitted to the sponsor as soon as it becomes available.

7.7.1.5 Sponsor Safety Reporting to Regulatory Authorities

Investigators are required to report all SAEs, including anticipated SAEs, to the sponsor (see Section [7.7.1.4](#)).

The sponsor will report all SAEs to regulatory authorities as required per local regulatory reporting requirements. In the United States, endpoints that assess disease-related mortality or major morbidity as well other SAEs that are not study endpoints, but are known consequences of the underlying disease or condition that are anticipated to occur in the study population should not be reported to the Food and Drug Administration (FDA) as individual Investigational New Drug (IND) safety reports per the final rule amending the IND safety reporting requirements under 21 CFR 312.32 and the FDA's guidance Safety Reporting Requirements for INDs and Bioavailability (BA) and Bioequivalence (BE) Studies (December 2012).

In this study, the SAEs that do not require individual IND safety reports to the FDA are progression of the underlying cancer. These anticipated SAEs will be reviewed periodically by the Seattle Genetics Drug Safety Department. If, upon review, an SAE is occurring at a higher rate than that which would be expected for the investigational arm (19A+RICE), then an IND safety report for the SAE will be submitted to the FDA.

7.7.2 Vital Signs

Vital signs measures are to include heart rate, blood pressure, and temperature. Vital signs should be collected per institutional standard for RICE infusion. For patients in the 19A+RICE Arm, vitals will be measured and recorded prior to the start of the denintuzumab mafodotin infusion and upon the completion of the infusion. All vitals should be measured after the patient has been sitting/resting for at least 5 minutes.

7.7.3 Clinical Laboratory Tests

Samples will be drawn for local labs. Local laboratory testing will include institutional standard tests for evaluating safety and making clinical decisions. The following laboratory assessments will be performed by the local lab to evaluate safety at scheduled timepoints (see [Appendix A](#)) during the course of the study:

- The chemistry panel includes, but is not limited to, the following tests: albumin, alkaline phosphatase, alanine aminotransferase (ALT), aspartate aminotransferase (AST), blood urea nitrogen, calcium, creatinine, chloride, glucose (fasting at baseline), lactate dehydrogenase (LDH), phosphorus, potassium, sodium, total bilirubin, and uric acid.
- Hgb A1c
- The CBC with differential is to include the following tests: white blood cell count with five-part differential (neutrophils, lymphocytes, monocytes, eosinophils, and basophils), platelet count, hemoglobin, and hematocrit. Manual differential should be completed when clinically indicated.
- PT/PTT/INR
- Hepatitis B surface antigen and anti-hepatitis B core antibody testing. If either is positive, PCR for hepatitis B viremia must also be performed.
- A serum or urine β -hCG pregnancy test for females of childbearing potential (FOCBP)
- Spot Urine. A spot urine will be performed to test urine samples for urine protein and creatinine values, and results will be used to calculate a UPC ratio.
- A 24-hour urine collection to test for total protein value will be required at visits where the UPC >2. If UPC >2 during a treatment cycle, only one 24-hour urine collection is required prior to the next cycle dosing.

7.7.4 Physical Examination

Physical examinations should include assessments of the following body parts/systems: abdomen, extremities, head, heart, lungs, neck, and neurological. Measurements of weight will be obtained. Measurements of height obtained within the prior 12 months may be utilized.

7.7.5 Ocular Monitoring Plan

In order to assess the effects of denintuzumab mafodotin on the eye, patients in both study arms will have complete ophthalmology assessments at protocol-defined timepoints (see Section 6 and [Appendix A](#)). Ophthalmology assessments are to include, but are not limited to, visual acuity and slit lamp examination. A baseline dilated fundus examination is required; subsequent dilated fundus examinations are to be conducted as clinically indicated. In particular, corneal epithelium changes must be assessed at each timepoint. Assessments must also include evaluation of steroid eye drop-induced changes including, but not limited to, intraocular pressure measurements and subcapsular cataracts. In addition, ophthalmologic evaluations will be obtained in the event of subjective visual or ocular disturbances while on study.

The results of the ophthalmological exam should be reviewed prior to the next dosing of denintuzumab mafodotin, and dose modifications of denintuzumab mafodotin should be made based on ocular toxicity grading of symptoms or corneal changes (see Section 5.8.1 and [Appendix E](#)) following discussion with the medical monitor.

Ophthalmology exams and ocular health surveys are required at baseline, the end of Cycles 2 and 3 (Days 15–21), EOT, and approximately 30-days post ASCT (for those patients who proceed to ASCT). In the event of ocular toxicity, ophthalmology exams should be conducted at least monthly during the follow-up period (unless discussed with the medical monitor) until resolution or return to baseline.

